6.4.6. Week 15 Contact

Subjects will be contacted on Day 105 (± 3 days) to review adverse events and concomitant medications, and to remind the subject to hold study drug dose on the day of the next visit so subject can take the study drug while on site.

6.4.7. Week 18 Visit

The Week 18 visit will occur on Day 126 (± 7 days). On the day of the visit, subjects should take study drug on site.

The following will be performed and documented at the Week 18 visit:

- Predose blood sample collection for plasma PK sample as described in Section 6.21. The first PK sample should be collected before the subject has taken the daily study drug dose at the site.
- Predose urine sample collection for urine PK as described in Section 6.21. The urine sample for PK should be collected before the subject has taken the daily study drug dose at the site.

- Blood and urine sample collection for Clinical Laboratory Assessments as described in Section 6.20
- Urine pregnancy test for females of childbearing potential only
- Witness daily study drug dosing after predose PK sample collection
- Abbreviated physical examination including vital signs as described in Sections 6.18 and 6.19
- Standard 12-lead resting ECG as described in Section 6.12
- ZIO[®] XT Patch wear starts at any time during the Week 18 visit and continues for 14 days. Subjects will be provided with instructions for wear and removal of the patch. The ZIO[®] XT Patch will be collected at the Week 24 visit.
- Review of concomitant medications
- Review of adverse events
- Collect and review used and unused study drug for accountability and calculate compliance
- Dispense study drug
- Second blood sample collection for plasma PK sample as described in Section 6.21. The second PK sample should be collected approximately 3 hours after the subject has taken the daily dose of study drug. If 3 hours postdose is not possible, the PK sample should be collected as late as possible before the subject leaves the clinic.
- Instruct the subject to hold the study drug dose on the day of the next visit so the subject can take the study drug while on site.

6.4.8. Week 21 Contact

Subjects will be contacted on Day 147 (± 3 days) to review ZIO[®] XT Patch wear/removal, adverse events and concomitant medications, remind the subject to hold study drug dose on the day of the next visit so subject can take the study drug while on site, and review CPET restrictions for the next visit.

6.4.9. Week 24 Visit

The Week 24 visit will occur on Day 168 (± 7 days). On the day of the visit, subjects should take study drug on site. If needed, the Week 24 visit may be conducted over 2 consecutive days.

In order to accumulate additional long-term safety in this population, subjects will continue double-blind treatment until the last subject has been followed up for approximately 24 weeks. As that date approaches, all remaining subjects (including subjects who have already discontinued treatment but who are continuing the study) will be contacted to return for the End of Double-Blind Treatment Period (EDBT) visit. For some subjects the Week 24 visit may also serve as the EDBT visit, see Section 6.4.11 for further detail.

Recommended order of assessments at Week 24 visit: (1) predose PK sample collection, (2) witnessed study drug dosing, (3) MLHFQ, (4) ECG, (5) CPET, (6) ECHO, and (7) all other blood sample collection including postdose PK sample. All other required visit assessments may occur at any point during the study visit. It is important that the MLHFQ administration occurs prior to CPET.

The following will be performed and documented at the Week 24 visit:

- Abbreviated physical examination including vital signs, as described in Sections 6.18 and 6.19
- Predose blood sample collection for plasma PK sample as described in Section 6.21. The first PK sample should be collected before the subject has taken the daily study drug dose at the site.
- Predose urine sample collection for urine PK as described in Section 6.21. The urine sample for PK should be collected before the subject has taken the daily study drug dose at the site.
- Witness daily study drug dosing after predose PK sample collection
- MLHFQ administration as described in Section 6.16
- Perception of Treatment Assignment Questionnaire administration as described in Section 6.17
- Standard 12-lead resting ECG as described in Section 6.12
- For subjects with ICDs, perform ICD interrogation as described in Section 6.15
- Cardiopulmonary Exercise Testing (CPET) using the Modified Naughton Protocol as described in Section 6.11 and according to the study-specific CPET Manual.
- ECHO as described in Section 6.14

- Blood and urine sample collection for Clinical Laboratory Assessments as described in Section 6.20
- Urine pregnancy test for females of childbearing potential only
- Blood sample collection for NT-proBNP and hsTnT testing
- Review of concomitant medications
- Review of adverse events
- Collect and review used and unused study drug for accountability and calculate compliance
- Dispense study drug
- Collect ZIO[®] XT Patch
- Second blood sample collection for plasma PK sample as described in Section 6.21. The second PK sample should be collected approximately 3 hours after the subject has taken the daily dose of study drug. If 3 hours postdose is not possible, the PK sample should be collected as late as possible before the subject leaves the clinic. If the subject is participating in the open-label extension, the second PK sample must be collected before the subject takes the blinded loading dose.
- Instruct the subject to hold the study drug dose on the day of the next visit so the subject can take the study drug while on site.

6.4.10. Post Week 24 Double-Blind Treatment Period Visits

Post Week 24 Double-Blind Treatment Period Visits will occur every 12 weeks (± 7 days) until the last subject has been followed up for approximately 24 weeks.

At each post Week 24 double-blind treatment period visit the following will be performed and documented:

- Predose blood sample collection for plasma PK sample as described in Section 6.21. The first PK sample should be collected before the subject has taken the daily study drug dose at the site.
- Predose urine sample collection for urine PK as described in Section 6.21. The urine sample for PK should be collected before the subject has taken the daily study drug dose at the site.
- Blood and urine sample collection for Clinical Laboratory Assessments as described in Section 6.20
- Urine pregnancy test for females of childbearing potential only

- Witness daily study drug dosing after predose PK sample collection
- Abbreviated physical examination including vital signs, as described in Sections 6.18 and 6.19
- Standard 12-lead resting ECG as described in Section 6.12
- Review of concomitant medications
- Review of adverse events
- Collect and review used and unused study drug for accountability and calculate compliance
- Dispense study drug
- Second blood sample collection for plasma PK sample as described in Section 6.21. The second PK sample should be collected approximately 3 hours after the subject has taken the daily dose of study drug. If 3 hours postdose is not possible, the PK sample should be collected as late as possible before the subject leaves the clinic.
- Instruct the subject to hold the study drug dose on the day of the next visit so the subject can take the study drug while on site.

6.4.11. End of Double-Blind Treatment (EDBT) Period Visit

Subjects will continue double-blind treatment until the last subject has been followed up for approximately 24 weeks. As that date approaches, all remaining subjects (including subjects who have already discontinued treatment but who are continuing the study) will be contacted to return for the End of Double-Blind Treatment Period visit. At this time, subjects due for their Week 24 visit should perform all Week 24 assessments and do not require an End of Double-Blind Treatment Period visit in addition. Subjects will continue to receive blinded study drug through the End of Double-Blind Treatment Period visit. On the day of the visit, subjects should take the daily maintenance dose of double-blind study drug at the site.

Subjects who have already discontinued treatment but who are continuing the study will also be contacted for the End of Double-Blind Treatment Period visit when the last subject is anticipated to complete the Week 24 visit.

The following procedures will be performed and documented at the End of Double-Blind Treatment Period visit:

- Predose blood sample collection for plasma PK sample as described in Section 6.21. The first PK sample should be collected before the subject has taken the daily study drug dose at the site.
- Predose urine sample collection for urine PK as described in Section 6.21. The urine sample for PK should be collected before the subject has taken the daily study drug dose at the site.

- Blood and urine sample collection for Clinical Laboratory Assessments as described in Section 6.20
- Urine pregnancy test for females of childbearing potential only
- Witness daily study drug dosing after predose PK sample collection
- Abbreviated physical examination including vital signs, as described in Sections 6.18 and 6.19
- Standard 12-lead resting ECG as described in Section 6.12
- Review of concomitant medications
- Review of adverse events
- Collect and review used and unused study drug for accountability and calculate compliance
- Second blood sample collection for plasma PK sample as described in Section 6.21. The second PK sample should be collected approximately 3 hours after the subject has taken the daily dose of study drug. If 3 hours postdose is not possible, the PK sample should be collected as late as possible before the subject leaves the clinic. If the subject is participating in the open-label extension, the second PK sample must be collected before the subject takes the blinded loading dose.
- If subject will participate in the open-label extension period, perform and document open-label entry procedures described in Section 6.5.1.

At the end of the double-blind treatment period, all subjects who complete the treatment period (including study drug dosing), may continue in the study at the discretion of the investigator, and receive GS-6615 in an open-label extension until this drug is commercially available for the treatment of patients with symptomatic HCM, or the investigator deems it no longer in the subject's best interests, or until Gilead terminates development of the study drug for the treatment of symptomatic HCM in the subject's home country. The expected maximum treatment duration is approximately 52 months (assuming a 12 month enrollment period, double-blind treatment up to maximum of approximately 20 months, and open-label treatment up to maximum of approximately 32 months).

6.5. Treatment Assessments: Open-label Extension

At the end of the double-blind, placebo-controlled treatment period all subjects who complete the treatment period (including study drug dosing), may continue in the study, at the discretion of the investigator, and receive GS-6615 in an open-label extension until this drug is commercially available for the treatment of patients with symptomatic HCM, or the investigator deems it no longer in the subject's best interests, or until Gilead terminates development of the study drug for the treatment of symptomatic HCM in the subject's home country.

6.5.1. Start of Open-label Extension Period (OLE)

At the end of the EDBT visit, subjects continuing into the open-label extension period the following will be performed and documented:

- Dispense study drug. Provide subject with dosing instructions for GS-6615 open-label extension.
- All subjects will take a blinded loading dose of study drug (GS-6615 or matching placebo) on site.
- Instruct the subject to hold the GS-6615 dose on the day of the next visit so the subject can take the study drug while on site.

6.5.2. Open-label Extension Period (OLE) Visits

GS-6615 open-label extension period visits will occur at the following time points: OLE Week 12 (OLE Day 84 ± 7 days), OLE Week 24 (OLE Day 168 ± 7 days), and every 24 weeks (± 14 days) thereafter (ie, OLE Week 48 and so on).

At each OLE visit the following will be performed and documented:

- PK sample collection at OLE Week 12 and OLE Week 24 visits:
 - Predose blood sample collection for plasma PK sample as described in Section 6.21. The first PK sample should be collected before the subject has taken the daily study drug dose at the site.
 - Predose urine sample collection for urine PK as described in Section 6.21. The urine sample for PK should be collected before the subject has taken the daily study drug dose at the site.
 - Witness daily study drug dosing after predose PK sample collection
 - Second blood sample collection for plasma PK sample as described in Section 6.21. The second PK sample should be collected approximately 3 hours after the subject has taken the daily dose of study drug. If 3 hours postdose is not possible, the PK sample should be collected as late as possible before the subject leaves the clinic.
- PK sample collection from OLE Week 48 visit through last OLE visit:
 - Plasma PK sample collection at a single timepoint at each visit as described in Section 6.21
- Blood and urine sample collection for Clinical Laboratory Assessments as described in Section 6.20

- Urine pregnancy test for females of childbearing potential only
- Abbreviated physical examination including vital signs, as described in Sections 6.18 and 6.19
- Standard 12-lead resting ECG as described in Section 6.12
- Review of concomitant medications
- Review of adverse events
- Collect and review used and unused study drug for accountability and calculate compliance
- Dispense study drug

6.5.3. OLE Week 1 Contact

Subjects will be contacted at OLE Week 1 (OLE Day 7 \pm 3 days) to review adverse events and concomitant medications.

6.6. Post-treatment Assessments

6.6.1. 30-day Follow-up Visit

Subjects will complete a safety follow-up visit 30 days (+7 days) after the last dose of study drug. Subjects who permanently discontinue study drug prior to Week 24 and continue to attend normal study visits (at minimum one visit at least 30 days after last dose) after study drug discontinuation are not required to complete the follow-up visit. Please refer to Section 6.8, Assessments for Premature Discontinuation from Study, for assessments for subjects who discontinue study participation in addition to discontinuing study drug prior to Week 24.

The following will be performed and documented at the safety follow-up visit:

- Abbreviated physical examination including vital signs, as described in Sections 6.18 and 6.19
- Standard 12-lead resting ECG as described in Section 6.12
- Blood and urine sample collection for Clinical Laboratory Assessments as described in Section 6.20
- Urine pregnancy test for females of childbearing potential only
- Plasma PK sample collection at a single timepoint as described in Section 6.21
- Review of concomitant medications

- Review of adverse events
- Additional unscheduled assessments may be performed at the discretion of the investigator (eg, for evaluation of AEs and laboratory abnormalities).

6.7. Unscheduled Visits

Additional unscheduled assessments may be performed at the discretion of the investigator (eg, for evaluation of AEs and laboratory abnormalities).

6.8. Assessments for Premature Discontinuation from Study

Please refer to Section 5.3.1, Dose Modification for Adverse Events, for down-titration and study drug interruption instructions.

If a subject permanently discontinues study drug dosing prior to Week 24, every attempt should be made to keep the subject in the study and continue to perform the required study-related follow-up and procedures until end of the double-blind treatment period. If this is not possible or acceptable to the subject or investigator, the subject will be withdrawn from the study.

If a subject permanently discontinues study drug dosing at or after Week 24, the 30-day Follow-up visit will be completed. Please refer to Section 6.6.1 for 30 day Follow-up visit details.

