5.1.1. Procedures for Breaking Treatment Codes

In the event of a medical emergency where breaking the blind is required to provide medical care to the subject, the investigator may obtain treatment assignment directly from the IXRS system for that subject. In case of technology failure, the investigator may obtain treatment assignment by contacting the IXR provider directly. Gilead recommends but does not require that the investigator contact the Medical Monitor before breaking the blind. Treatment assignment should remain blinded unless that knowledge is necessary to inform emergency medical care. The rationale for unblinding must be clearly explained in source documentation and on the case report form/ electronic case report form (CRF/eCRF), along with the date on which the treatment assignment was obtained. The investigator is requested to contact the Medical Monitor within 24 hours upon any instances of treatment unblinding.

Blinding of study treatment is critical to the integrity of this clinical trial and therefore, if a subject's treatment assignment is disclosed to the investigator, the subject will have study treatment discontinued. All subjects will be followed until study completion unless consent to do so is specifically withdrawn by the subject.

Gilead Drug Safety and Public Health (DSPH) may independently unblind cases for expedited reporting of suspected unexpected serious adverse reactions (SUSARs).

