5.3.1. Dose Modification for Adverse Events

The investigator is encouraged to manage adverse events (depending on their severity) with standard medical therapy prior to consideration of dose modification.

Down-titration or interruption of study drug is discouraged but permitted if necessary in the event of intolerance to study drug. Subsequent up-titration of study drug back to the target dose should be attempted whenever possible.

If it is believed that an adverse event may be drug-related, and depending on its severity, and with approval by the Medical Monitor, the study drug may be:

- reduced from 2 tablets once daily to 1 tablet once daily
- interrupted temporarily with a plan to re-initiate treatment
- discontinued permanently

Subjects who are unable to tolerate a dose of 1 tablet once daily will discontinue study drug dosing. If a subject discontinues study drug dosing, every attempt should be made to keep the subject in the study and continue to perform the required study-related follow-up and procedures through Week 24.

Subjects who complete the Week 12 visit but are unable to consistently tolerate 1 tablet once daily should continue on no more than 1 tablet of blinded study drug once daily after Week 12. After a period of consistent tolerability at the dose of one tablet once daily, the subject may attempt to up-titrate to the target dose of 2 tablets once daily, at the discretion of the investigator and in consultation with the Medical Monitor.

Subjects who complete the double-blind treatment period at a down-titrated dose of 1 tablet of blinded study drug once daily may continue into the open-label extension at 3 mg once daily of GS-6615. After a period of consistent tolerability at the dose of 3 mg once daily, the subject may attempt to up-titrate to the target dose of 6 mg once daily, at the discretion of the investigator and in consultation with the Medical Monitor.

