6.10. End of Study

End of study is defined as the last subject's last visit (ie, 30-day Follow-up visit). The expected maximum treatment duration is approximately 52 months (assuming a 12 month enrollment period, double-blind treatment up to maximum of approximately 20 months, and open-label treatment up to maximum of approximately 32 months).

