7.1.6. Summaries of Adverse Events and Deaths

A brief summary of AEs will show, by treatment group, the number and percentage of subjects who (1) had any treatment-emergent AE, (2) had any treatment-emergent moderate or severe AE, (3) had any treatment-emergent severe AE, (4) had any treatment-emergent treatment-related AE, (5) had any treatment-emergent treatment-related moderate or severe AE, (6) had any treatment-emergent treatment-related severe AE, (7) had any treatment-emergent SAE, (8) had any treatment-emergent treatment-related SAE, (9) permanently discontinued from study drug due to an AE, (10) had dose reduced or temporarily interrupted due to an AE, and (11) died during study.

The number and percentage of subjects who experienced at least 1 TEAE will be provided and summarized by SOC, HLT and PT. For other AEs described below, summaries will be provided by SOC and PT, and/or by PT as indicated:

- All treatment-emergent AEs by severity
- All treatment-emergent AEs (by PT)
- All treatment-emergent treatment-related AEs (and by PT)
- All treatment-emergent serious AEs (and by PT)
- All treatment-emergent treatment-related SAEs (and by PT)
- All treatment-emergent AEs that caused permanent discontinuation from study drug
- All treatment-emergent AEs that caused temporary interruption of study drug
- All treatment-emergent AEs that caused dose reduction of study drug
- All treatment-emergent AEs that caused permanent discontinuation from study
- All treatment-emergent AEs leading to death

Multiple events will be counted once only per subject in each summary. For data presentation, SOC and HLT will be ordered alphabetically, with PT sorted by decreasing total frequency. For summaries by severity grade, the most severe event will be selected. In addition to the presentation by SOC and HLT, all treatment-emergent AEs will also be presented by preferred term only, ordered by decreasing total frequency.

In addition to the by-treatment summaries, data listings will be provided for the following:

- All AEs (with a flag indicating whether the event is treatment-emergent)
- SAEs (including deaths)
- Subjects who became pregnant during the study
- AEs leading to discontinuation of study or study drug
- Severe AEs
- AEs leading to temporary interruption of study drug
- AEs leading to dose reduction
- AEs leading to death

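### Protocol 5.3.1 and 6.8 disagree on how long subjects who stop drug before Week 24 are followed, 6.8 is silent on follow-up after the 30-day visit for later stoppers, and the SAP death count has no end date

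*Protocol*

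**What the plan says.** On subjects who stop study drug, the protocol says the following.

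- Section 5.3.1: sites should try to retain the subject, who is to "continue to perform the required study-related follow-up and procedures through Week 24".
- Section 6.8, stop before Week 24: the subject is to "continue to perform the required study-related follow-up and procedures until end of the double-blind treatment period".
- Section 6.8, stop at or after Week 24: "If a subject permanently discontinues study drug dosing at or after Week 24, the 30-day Follow-up visit will be completed". Nothing is said about what comes after that visit.
- Section 6.6.1: "Subjects will complete a safety follow-up visit 30 days (+7 days) after the last dose of study drug". Subjects who stop before Week 24 and keep attending visits are exempt.
- Section 6.4.11: "Subjects who have already discontinued treatment but who are continuing the study will also be contacted for the End of Double-Blind Treatment Period visit". There is no split by date of stopping.
- Section 5.1.1, on subjects taken off drug after unblinding: "All subjects will be followed until study completion unless consent to do so is specifically withdrawn by the subject".
- Section 6.8.2: vital status is collected every 3 months to the end of the double-blind period for subjects who terminate early, are lost or withdraw consent, once they have agreed to it. Section 6.8.1 takes that consent at the Early Termination (ET) visit.

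In SAP 7.1.6 the brief adverse-event summary by treatment group ends with the item "and (11) died during study". No window or end date is attached.

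**The concern.** Mortality heads the safety endpoints in Protocol 8.1.5, and double-blind treatment was carried past Week 24 in order to gather long-term safety data. That aim needs a clear rule on how long subjects off drug are observed. Two sections give different rules for the same early stopper, and the rule for late stoppers is incomplete. Two sites could follow similar subjects for very different lengths of time, each in good faith. A death count without an end date then depends partly on when the subject stopped and which section the site applied. If late stopping were more common in one arm, that arm would have less time in which deaths could be recorded.

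**Working it through.** The plan gives no figure of its own here, so the check sets the rules side by side and converts them to weeks.

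**Inputs**
- Planned double-blind maximum: about 20 months (Protocol 3.2) = 20 x 365.25/12/7 = 87 weeks. The last target visit in SAP Table 3-4 is Week 84. I use both as a range.
- 30-day visit, with its +7 days (Protocol 6.6.1): 30/7 = 4.3 to 37/7 = 5.3 weeks after last dose.
- SAEs and deaths reportable for everyone within 60 days of last dose (Protocol 7.3): 60/7 = 8.6 weeks.

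**Stop before Week 24 (direct conflict)**
- Stop at Week 23: 24 - 23 = 1 week under 5.3.1; 84 - 23 = 61 to 87 - 23 = 64 weeks under 6.8.
- Stop at Week 4: 24 - 4 = 20 weeks under 5.3.1; 84 - 4 = 80 to 87 - 4 = 83 weeks under 6.8.
- For the last subject enrolled, whose double-blind period is about 24 weeks, the two rules coincide.

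**Stop at Week 24 (incomplete rule)**
- If follow-up ends with the 30-day visit: 4.3 to 5.3 weeks.
- If the subject counts as still in the study and returns under 6.4.11: 84 - 24 = 60 to 87 - 24 = 63 weeks.

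For an early enrollee, required follow-up can therefore drop from 61-64 weeks to 4-5 weeks across Week 24. On the protocol's assumed 12-month enrolment, the longest double-blind period is 52.2 + 24 = 76.2 weeks, and the 61-64 becomes 76.2 - 23 = 53 weeks.

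**Does vital status close the gap?** Section 6.8.1 triggers the ET visit when a subject leaves the study at any time in the double-blind period. Appendix 2 footnote b limits it to subjects leaving before completing 24 weeks. On the first reading a late stopper who leaves the study is asked for vital-status consent; on the second, not. Neither 6.6.1 nor the late-stop rule in 6.8 mentions vital status.

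**Which outputs are exposed?** Treatment-emergent events end 30 days after last dose for every subject (Protocol 8.6.2, SAP 7.1.5.1). The SAP tables of SAEs and of adverse events leading to death are restricted to those events, so they do not move with the rule applied. What can move is item 11 of SAP 7.1.6, and SAEs later than the reporting windows, which appear in listings.

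**Scale, on assumed stopping.** Suppose 10% per arm, 9 of 90, stop after Week 24, and observation ends at 30 days.
- Extreme: all nine are among the first enrolled and stop at Week 25. Observation ends at about Week 29 (25 + 4.3); 84 - 29 = 55 weeks; 9 x 55 = 495 subject-weeks per arm.
- More even: double-blind lengths uniform from 24 to 84 weeks and a constant stopping rate after Week 24. Remaining time r then has density proportional to 60 - r on 0 to 60. The mean excess over 4.3 weeks is [(60 - 4.3)^3 / 6] / (60^2 / 2) = 28,801 / 1,800 = 16 weeks, and 9 x 16 = 144 subject-weeks per arm.

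**The case against.** Several stronger readings are tempting, and the documents do not support them.

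- A reader might infer four competing follow-up lengths for one subject. The two rules in 6.8 cover different groups, 5.1.1 sits in the section on unblinding, and 6.4.11 is limited to subjects still in the study. The direct contradiction is between 5.3.1 and 6.8 for stops before Week 24; 5.1.1 adds to it only for an unblinded subject.
- A reader might infer that the SAE tables are distorted. They are not: one 30-day cut-off applies to everyone, and SAEs and deaths within 60 days of last dose are reportable whenever the stop occurred.
- A reader might take 6.8 to end follow-up at the 30-day visit for late stoppers. It names the visit without saying that follow-up then stops, and 6.6.1 gives a reason for naming it, since early stoppers who keep attending are exempt.
- A reader might say that late stoppers have no ET visit. Section 6.8.1 allows one throughout the double-blind period, and it makes some ET assessments conditional on leaving before Week 24, which implies that later ET visits occur. Only footnote b points the other way.
- The 495 subject-weeks is an upper bound, more than three times the 144 under even enrolment.

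It is also fair to say that no formal safety comparison is planned (Protocol 8.6, SAP 7), that nothing in the documents suggests late stopping differs by arm, and that SAP Section 2 records early termination by the sponsor. These points limit the size of the problem and what can still be repaired. They do not remove the conflict between 5.3.1 and 6.8, the silence after the 30-day visit, or the missing end date for deaths.

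**Conclusion.** The point holds in limited form. Sections 5.3.1 and 6.8 cannot both be followed for a subject who stops before Week 24, except where the double-blind period itself ends at about Week 24. For later stops the length of follow-up is undefined beyond 30 days, and vital-status cover depends on which ET rule a site reads. The step from 61-64 to 4-5 weeks describes an early enrollee on the planned schedule. It shrinks for later enrollees, and early termination probably reduced it further, though actual dates are not given.

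The consequence is confined to the unwindowed death count and to late SAEs in listings. Few deaths are likely to be involved. A biased comparison would also require more late stopping in one arm, which is a possibility and not a finding. The subject-week figures rest on an assumed 10% late stopping. This is worth correcting because it is cheap and concerns a leading safety endpoint, but it does not put the trial's main safety tables in doubt.

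**What to change.** **SAP, still actionable.** In 7.1.6 item 11, count deaths among all randomised subjects by assigned arm up to one common date, either the double-blind end or the study termination date. Show deaths within 30 days of last dose as a separate line. State how many subjects per arm have known vital status at the common date, since the count can include only deaths that were captured. SAP 7.9 also reports deaths without a window and should use the same date. The cost is a few table lines, to be settled before the blind is broken.

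**Protocol, for the record or for a similar trial.** Reconcile 5.1.1, 5.3.1, 6.4.11, 6.6.1, 6.8, 6.8.1, 6.8.2 and Appendix 2 footnote b into one data-collection rule for subjects off drug. The sponsor must decide which visits apply. At a minimum, the existing 3-monthly vital-status contact should run to the double-blind end date for late stoppers too, unless consent is withdrawn, with that consent obtained at a visit they actually have. The cost is amendment wording and a few extra contacts. It cannot recover follow-up already lost, and it changes nothing about treatment.
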